6.8.3 Prohibited Medications

To be enrolled in the study participants must:

- Be willing to comply with all medication requirements per protocol.

7.0 Discontinuation of Study Intervention and Participant Discontinuation/Withdrawal

Discontinuation of the site or study as a whole is detailed in [Appendix 1: Regulatory, Ethical, and Study Oversight Considerations](#).

7.1 Discontinuation of Study Intervention

In rare instances, it may be necessary for a participant to permanently discontinue study Dosing Sessions. If the Dosing Sessions are permanently discontinued, the participant may remain in the study and continue with the optional Integration Session. If the investigator determines it is in the participant's best interest to completely withdraw from the study, an early discontinuation visit should be conducted, defined as all the procedures included in the End of Study Visit.

7.1.1 QTc Stopping Criteria

If a clinically significant finding is identified (including, but not limited to, changes from baseline in QT interval corrected using Fridericia's formula [QTcF]) after enrollment, the investigator or qualified designee will determine if the participant can continue in the study and if any change in participant management is needed. This review of the ECG printed at the time of collection must be documented. Any new clinically relevant finding should be reported as an AE.

A participant who meets either bulleted criterion based on multiple ECG readings will be withdrawn from study intervention.

- QTc >500 ms OR Uncorrected QT >600 ms
- Increase from baseline of QTc >60 ms

7.2 Participant Discontinuation/Withdrawal from the Study

A participant may withdraw from the study at any time at their own request or may be withdrawn at any time at the discretion of the investigator for safety, behavioral, or compliance reasons. This is expected to be uncommon.

- At the time of discontinuing from the study, if possible, an early discontinuation visit should be conducted, defined as all the procedures included in the End of Study Visit.
- The participant will be permanently discontinued from the study intervention and the study at that time.

- If a participant develops any Exclusion Criteria that, in the opinion of the Medical Monitor or Site, affects the safety of the participant, the participant will not receive any additional IMP but will complete the remaining procedures in that Dosing Session, and an End of Study Visit.
- If the participant withdraws consent for disclosure of future information, the sponsor may retain and continue to use any data collected before such a withdrawal of consent.
- If a participant withdraws from the study, they may request destruction of any samples taken and not tested, and the investigator must document this in the site study records.

7.3 Lost to Follow-up

A participant will be considered lost to follow-up if they repeatedly fail to return for scheduled visits and is unable to be contacted by the study site.

The following actions must be taken if a participant fails to return to the clinic for a required study visit:

- The site must attempt to contact the participant and reschedule the missed visit as soon as possible, counsel the participant on the importance of maintaining the assigned visit schedule and ascertain whether the participant wishes to and/or should continue in the study.
- Before a participant is deemed lost to follow-up, the investigator or designee must make every effort to regain contact with the participant (e.g., three telephone calls or emails). In addition, site shall reach out to the contact person (relative, spouse, close friend, or other support person) provided by the participant. Finally, if necessary, a certified letter to the participant's last known mailing address or local equivalent methods. These contact attempts should be documented in the participant's medical record.
- Should the participant continue to be unreachable, they will be considered to have withdrawn from the study.

8.0 Study Assessments and Procedures

- Protocol waivers or exemptions are not allowed.
- Immediate safety concerns should be discussed with the sponsor immediately upon occurrence or awareness to determine if the participant should continue or discontinue study intervention.
- Adherence to the study design requirements is essential and required for study conduct.
- All screening evaluations must be completed and reviewed to confirm that potential participants meet all eligibility criteria. The investigator will maintain a screening log to record details of all participants screened and to confirm eligibility or record reasons for screening failure, as applicable.
- Procedures conducted as part of the participant's routine clinical management (e.g., blood count) and obtained before signing of the ICF may be utilized for screening or baseline purposes provided the procedures met the protocol-specified criteria.

8.1 Screening Period

Prospective participants may be pre-screened by telephone to ascertain if they meet basic eligibility criteria. Data from potential participants who do not pass telephone screening will not be entered in the eCRF, but reason of ineligibility will be documented on a Telephone Screening Log.

Participants who are preliminarily eligible following the telephone screen will be invited to screen for the study. Site staff (preferably a member of the team who would be treating this potential participant) will explain and obtain written (or electronic) informed consent using the IRB-approved ICF. Written consent must be obtained prior to performing any tests or evaluations for the study. The signature may be obtained using an electronic 21 CFR Part 11 compliant system due to COVID-19. Discussion about the ICF may take place over a telemedicine visit or at the first in-person visit. If a participant fails Screening and is rescreened at a later date, a new copy of the ICF should be signed.

All individuals who are screened should be assigned a Screening Number and recorded on the Screening Log.

At any time during Screening, if a potential participant is deemed ineligible, they will be classified as a Screen Failure, notified that they are not eligible for the study, and not be scheduled for any additional Screening assessments. Participants who are eligible by pre-screening will be invited to undergo the informed consent process, either in-person or via telemedicine as allowed per local and study site regulations.

Screening may take place over multiple visits and will be completed in-person, via tele-assessment, or over the telephone. Medical records, if available, should be requested from the participant's general practitioner to ensure a comprehensive medical history has been obtained.

8.1.1 Enrollment

Participants who meet all eligibility criteria and are randomized to a treatment assignment will be considered enrolled in the study. Participants who meet all eligibility criteria but who are subsequently not randomized will be classified as screen failures.

8.2 Preparation Session

Participants will undergo one 90-minute Preparation Session via telemedicine prior to the first Dosing Session. During this session, a MAPS-trained individual will work with the participant to prepare for the psychological effects of MDMA, promote a safe set and setting for confronting any unexpected memories, emotions, and thoughts, and introduce and offer the optional post-dose Integration Session.

8.3 Dosing Period

8.3.1 Dosing Sessions

There will be two open-label Dosing Sessions. Procedures for each dosing session are the same, except for the meal during the fed treatment. Participants will be randomized to first treatment. Dosing Sessions must be at least 8 hours long, measured from 30 minutes prior to IMP administration. At both Dosing Sessions, a dose of 100 mg MDMA (equivalent to 120 mg MDMA HCl) will be administered.

Study team will call participants 7 days prior to CRU check-in to remind them to stop any smoking or use nicotine containing products, if applicable.

8.3.1.1 Check-in to CRU

Participants will arrive at the CRU the night prior to IMP administration.

- The site team will ensure the participant fasts for at least 10 hours prior to IMP administration and agrees to comply with all other requirements per [Section 5.3 Lifestyle Considerations](#).
- The site team will inquire about any possible changes in health and concomitant medications to ensure the participant continues to meet all eligibility requirements and record AEs, as described in [Section 8.7.5 Method of Detecting AEs and SAEs](#).
- The site team will complete symptom-directed physical exam, urine drug screen, urine nicotine/cotinine screen, alcohol screen, pregnancy test (for PABP only), and concomitant medication review.
- The site team will measure blood pressure, body temperature, and pulse.
- The site team will administer Since Last Visit C-SSRS.
- A symptom-directed physical examination, or additional vital signs measurements, may be conducted at any time if clinically indicated.

8.3.1.2 Pre-IMP administration

Prior to each Dosing Session:

- The site team will inquire about any possible changes in health and concomitant medications to ensure the participant continues to meet all eligibility requirements and record AEs, as described in [Section 8.7.5 Method of Detecting AEs and SAEs](#).
- The site team will review procedures for the Dosing Session with the participant and some of the commonly experienced effects of MDMA.
- The site team will administer Since Last Visit C-SSRS.
- Ninety minutes to two hours prior to IMP administration, the site team will collect baseline measures:
 - Collect PK samples
 - Measure blood pressure, body temperature, and pulse
 - Administer a 12-lead ECG (in triplicate)
 - Administer the Subjective Effects VAS
- Thirty minutes prior to IMP administration, for Fed Treatments only:
 - Participants will begin eating a high-fat and high-calorie meal, see [Section 8.3.2 Pre-IMP Meal](#).

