3.0 Objectives and Endpoints

The overall objective of this pharmacokinetic study is to assesses the effect of food on the relative bioavailability of MDMA in healthy volunteers.

Table 2: Objectives and Endpoints

Objectives	Endpoints
Primary	
To evaluate the effect of a high fat (high calorie) meal as compared to administration in the fasted state on the relative bioavailability of oral MDMA capsules in healthy volunteers.	PK parameters determined for MDMA and its active metabolite MDA: area under the concentration-time curve from dosing time to last measurement time (AUC_{0-t}), area under the concentration-time curve from dosing time to infinity ($AUC_{0-\infty}$), and peak concentrations (C_{max}).
Safety	
To characterize the cardiac-related effects of MDMA by collecting supportive ECG data.	Mean change from baseline QT interval corrected for heart rate.
To observe the rates of treatment emergent adverse events of special interest that would reflect a serious arrhythmia or suggest the potential for such an arrhythmia.	The rates of the following events: 
 • Torsade de pointes (TdP) • Sudden death • Ventricular tachycardia • Ventricular fibrillation and flutter • Syncope of cardiovascular etiology
To evaluate the effect of MDMA and its active metabolite MDA, on hemodynamic parameters compared to baseline when administered to healthy volunteers.	Change from baseline in basal (resting) hemodynamic parameters: heart rate (HR) systolic blood pressure (SBP), diastolic blood pressure (DBP).

To further evaluate the safety and tolerability of MDMA in both fed and fasted states.	Incidence of adverse events, clinical laboratory test results, and vital sign measurements (body temperature).
Exploratory	
To further characterize the subjective effects of MDMA.	Change in subjective effects (self-reported VAS) from pre-dose to multiple timepoints post-dose.

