8.3.1.3 During the Dosing Session

During each Dosing Session:

- The site team will administer the study IMP with 240 mL of water.
- The participant will sit or recline on comfortable furnishings. Participants will be encouraged to bring items to each dosing session which will provide comfort while under the effects of MDMA. This may include comfortable clothes, a personal pillow, soft blanket, music, art supplies, or other supplies to engage in light recreational activities. Eyeshades and a program of music will be provided for the participant if they wish to use them.
- Water will be provided throughout the session at a paced intake, not to exceed three liters overall.

- The site team will collect the following measures at the following timepoints after IMP administration: 30 minutes, 1, 2, 4, 6, 8, 12 hours.
 - Collect PK samples
 - Measure blood pressure, body temperature, and pulse
 - Administer a 12-lead ECG (in triplicate)
 - Measure Subjective Effects VAS
- **Note:** when multiple assessments are scheduled at the same timepoint, the above order of assessments should be observed, so that the PK sample is collected as close to the exact timepoint as possible.
- No food should be allowed for at least 4 hours post-dose. A mid-day meal may be offered at least 4 hours after medication administration, and an evening meal may be offered 4 hours later.
- A member of the site team will remain available to the participant throughout the Dosing Session, see [Section 8.3.3 Psychological Support During Dosing Session](#).

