8.3.1.5 Post-Dosing Sessions

Participants will stay in the CRU for at least 36 hours following Dosing Session.

- An optional Integration Session will be offered 24 hours post-IMP to the participant, see [Section 8.3.5 Integration Session](#).
- Following collection of samples and assessments 48 hours post-IMP, participant will be discharged from CRU.
- Participants will return on 72 hours post-IMP for sample collection and assessments.
- The site team will collect the following measures at the following timepoints after IMP administration: 24 hours post-IMP, 48 hours post-IMP, and 72 hours post-IMP.
 - Collect PK samples
 - Measure blood pressure, body temperature, and pulse
 - Administer a 12-lead ECG (in triplicate)
 - Administer Since Last Visit C-SSRS
- Meals are not restricted after the Dosing Sessions.

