8.3.2 Pre-IMP Meal

A high-fat (approximately 50 percent of total caloric content of the meal) and high-calorie (approximately 800 to 1000 calories) meal will be used as a test meal for food-effect evaluation. The targeted macronutrient allocation for the calories of this test meal is as follows: protein (150 calories), carbohydrates (250 calories), and fats (500-600 calories). Following an overnight fast of at least 10 hours, participants will start the recommended meal 30 minutes prior to administration of the drug product. Participants will eat this entire meal in 30 minutes or less.

- An example test meal would be two eggs fried in butter, two strips of bacon, two slices of toast with butter, four ounces of hash brown potatoes and eight ounces of whole milk. Substitutions in this test meal can be made as long as the meal provides a similar number of calories from protein, carbohydrate, and fat and has comparable meal volume and viscosity.

The start and stop time of the start of the high-fat high-calorie pre-dose meal must be recorded. The percent of the total meal consumed by the end of the 30-minute eating period should be recorded. This percentage may be estimated by the study staff.

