8.5 Study Assessments

8.5.1 Primary Outcome Measure

8.5.1.1 PK Blood Sampling

PK samples to determine the bioavailability of MDMA and its metabolites will be collected.

Blood samples will be collected for the determination of plasma concentrations and PK. Additionally, at the occurrence of an SAE, unscheduled blood samples should be collected as soon as possible relative to the event. Blood samples will be collected via a saline flush catheter or by direct venipuncture.

At each timepoint, approximately 2 mL of blood will be collected for the analysis of plasma MDMA and MDA concentrations. Samples will be collected in blood collection tubes containing EDTA K₂ anticoagulant, inverted several times, and immediately placed in an ice bath. The clock times of all blood draws will be recorded and reported for each subject. All tubes will be labeled with a bar code. When scanned, the bar code will provide the SUBJID, protocol ID, anticipated blood draw time point, and actual collection time. Samples should be stored at -20/70° C until it will be transported to the lab for analysis.

The total volume of blood collected for MDMA and MDA PK analysis is approximately 22 mL (11 samples over a period of 72 hours).

Blood samples for determination of plasma concentrations of study drug/metabolite will be analyzed at off-site contract laboratories designated by the sponsor. Samples will be analyzed using a validated bioanalytical method.

When multiple assessments are scheduled at the same timepoint, the following order of assessments should be observed, so that the PK sample is collected as close to the exact timepoint as possible:

1. PK or blood sample
2. Vital Signs

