9.3.3 Safety Analyses

Safety and tolerability will be evaluated. Safety analyses include change from Baseline blood pressure, pulse, and temperature values at specified time points. All laboratory results and vital sign measurements will be summarized using appropriate descriptive statistics.

Adverse event (AE) data will be descriptively evaluated. Descriptive statistics (e.g., number of observations, means, standard deviations, medians, maximum and minimum values) will be used to summarize continuous variables. Frequencies, proportions, and the exact 95% confidence intervals (CI), when appropriate, will be used to summarize categorical variables. Subject listings will also be provided.

Suicidal ideation and behavior will be summarized according to suggestions made in the C-SSRS Scoring and Data Analysis Guide. The number and percent of positive responses of Positive Ideation, Serious Ideation, and Positive Behavior will be tabulated by treatment group and time period (lifetime, screening, baseline, each Dosing Session (pre- and post-IMP), Integrative Sessions, and endpoints). Frequency and incidence of positive or serious ideation and suicidal behavior will be presented using descriptive statistics in tabular format.

ECG analysis: Mean of the triplicate ECGs at each nominal time point will be used for all reporting and analysis; however, individual values will be used to calculate the correction coefficient (γ) for the individual correction QTc (QTcI). Individual correction coefficient, γ , will be estimated using linear regression of log QT on log RR for each subject using all baseline ECG assessments collected before Day 1 dosing within a subject.

The QTc corrections will be individual correction by QTcI = QT/RR^γ , Fridericia's by QTcF = $QT/RR^{0.33}$, and Bazett's by QTcB = $QT/RR^{0.5}$.

Change from baseline ($\Delta QTcI$) will be calculated as the average of the three predose assessments on Day 1 subtracted from the value (i.e., QTc) on Day 1 at a given time t . The effect of MDMA on cardiac repolarization will be assessed, as measured by the time point with the largest upper one-sided 95% confidence limit for the $\Delta QTcI$. The relationship between $\Delta QTcI$ (dependent variable) and MDMA or MDA concentrations (independent variable) will be determined using a linear mixed-effects model.

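### In fed sessions the Day 1 vital-sign and ECG baseline is taken before the test meal, so change from baseline there is MDMA plus meal, although the protocol attributes it to MDMA

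*Protocol*

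**What the plan says.** The timing comes from the protocol's procedures.

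- **Baseline, both sessions (8.3.1.2):** "Ninety minutes to two hours prior to IMP administration, the site team will collect baseline measures". The set comprises blood pressure, temperature, pulse and a triplicate 12-lead ECG.
- **Meal (8.3.1.2):** "Thirty minutes prior to IMP administration, for Fed Treatments only", the participant starts the test meal. Section 8.3.2 puts it at roughly 800 to 1000 calories and adds: "Participants will eat this entire meal in 30 minutes or less".
- **Day 1 readings (8.3.1.3):** "after IMP administration: 30 minutes, 1, 2, 4, 6, 8, 12 hours".
- **Later readings (8.3.1.5):** "24 hours post-IMP, 48 hours post-IMP, and 72 hours post-IMP".

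The attribution comes from the objectives and the analysis section.

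- **Table 2, section 3.0:** one safety objective is "To evaluate the effect of MDMA and its active metabolite MDA, on hemodynamic parameters compared to baseline".
- **Section 9.3.3:** the QTcI change uses "the average of the three predose assessments on Day 1 subtracted from the value" at each time on Day 1. The time point with the largest upper confidence limit is then taken as the measure of MDMA's effect on repolarization. Vital signs are also analysed as change from baseline. Neither statement mentions fed or fasted condition, whereas section 9.3.2 separates the two conditions for PK.

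**The concern.** A change from baseline can be credited to the drug only if nothing else of consequence happens between the baseline and the later reading. In fed sessions something does: a large meal, which may itself alter heart rate, blood pressure and, through heart rate, the QT correction. Section 8.3.1 says the two sessions differ only by the meal, and no period gives the meal without the drug, so fed-session data alone cannot separate the two effects.

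The safety statements about MDMA are what is at stake: the hemodynamic objective, the QTcI change by time point, and the concentration-QTc relationship. If fed sessions enter these without distinction, a meal response would be reported as a drug response. In the concentration-QTc model, condition may be related both to concentration and to heart rate. A model without a condition term could then fold part of the meal's effect into the concentration slope.

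**Working it through.** **1. Is there a second, post-meal baseline?** Count the scheduled collection times per session: 1 pre-dose (8.3.1.2) + 7 on Day 1 (8.3.1.3) + 3 later (8.3.1.5) = 11. At about 2 mL each (8.5.1.1), 11 × 2 = 22 mL. This reproduces the protocol's own figure, "approximately 22 mL (11 samples over a period of 72 hours", with exactly one pre-dose time. Vital signs and ECG are listed at the same times as the PK samples, so the schedule contains no reading between meal and dose.

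Other early readings do not change this. Vital signs at check-in (8.3.1.1) are taken the night before, screening ECGs (Table 1) are earlier still, and extra vital signs are taken only if clinically indicated. The three pre-dose assessments in 9.3.3 read naturally as the one triplicate. If three separate times were meant, none is scheduled after the meal.

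**2. Timeline in minutes from dosing.**

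| Event | Time |
|---|---|
| Baseline | −120 to −90 |
| Fed meal starts | −30 |
| Dose | 0 |
| First post-dose reading | +30 |

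- Baseline to meal start: −30 − (−90) = 60, up to −30 − (−120) = 90 minutes.
- Baseline to first post-dose reading: 30 + 90 = 120, up to 30 + 120 = 150 minutes.
- Meal start to the Day 1 readings (60t + 30, with t in hours after dosing): 60, 90, 150, 270, 390, 510 and 750 minutes.

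Every fed-session reading on Day 1 therefore follows the meal, and every fed-session baseline precedes it.

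**3. What each contrast contains.** Assume additivity. Let D_fed(t) and D_fast(t) be MDMA's own effect in each condition and m(t) the test meal's own effect.

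- Fasted change = D_fast(t)
- Fed change = D_fed(t) + m(t)
- Balanced pooled change = [D_fed(t) + D_fast(t)]/2 + m(t)/2
- Fed minus fasted = [D_fed(t) − D_fast(t)] + m(t)

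The documents give no value for m. Purely as an illustration, let m run from −10 to +10 units (bpm, mmHg or ms). As an estimate of MDMA's own effect, the fed change is then off by −10 to +10 and a balanced pooled change by −5 to +5. Both errors are zero only if m = 0.

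**4. Is a meal-free estimate available?** Yes. In fasted sessions no food is allowed for at least 4 hours after dosing (5.3.1, 8.3.1.3). Section 2.2.1 places peak effects at 1.25 to 2 hours, inside that window. After 4 hours meals may be offered in both conditions, so the 6, 8 and 12 hour readings may carry some meal effect in either session.

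**5. Precision cost of using one session.** With equal variance and between-session correlation ρ ≥ 0, the standard error of a one-session mean relative to a two-session mean is √[2/(1 + ρ)]. At ρ = 0 this is √2 ≈ 1.41. At ρ = 1 it is 1.

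**The case against.** The strongest reply is that much of this could be settled in the SAP, which is not shown. Section 9.0 promises more technical detail there, by-condition tables and model terms are usual SAP content, and no section says that fed and fasted sessions will be pooled. Section 9.2 analyses participants by the intervention actually received, and Table 2 asks for safety in both states. This stands as far as pooling goes: m/2 is a conditional figure. It does not remove the point, because the protocol itself fixes the baseline time, the baseline definition and the attribution to MDMA.

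A reader might go further and infer that the fed-minus-fasted safety comparison is biased. The documents do not support that. Sections 2.1 and 4.2 give the secondary purpose as the effect of food on MDMA's safety and tolerability. On a plain reading this is the total effect of dosing with a meal, and the meal's own contribution belongs in it. A common pre-meal baseline keeps that comparison like for like. What the difference cannot show is that food alters MDMA's own cardiovascular effect.

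Two further objections stand. Any specific bpm or ms figure for the meal is an assumption, since neither size nor sign is documented. And a single condition term in the concentration-QTc model removes only a constant shift, whereas a meal effect may vary over the 12 hours of Day 1.

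**Conclusion.** The point holds for fed-session change from baseline. In heart rate, systolic and diastolic pressure and QTcI, it measures MDMA and meal together, while Table 2 and section 9.3.3 attribute change from baseline to the drug without naming the condition. The error as an estimate of MDMA's own effect is m in fed sessions, and m/2 in a balanced pooled estimate if one were made. This rests on additivity and on m being non-zero; its size and direction are unknown.

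The finding is limited. It does not show that the protocol pools the sessions or that the fed-versus-fasted safety comparison is invalid for its stated purpose. The planned fasted sessions already provide a meal-free MDMA estimate through at least 4 hours after dosing. The primary PK comparison is unaffected.

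**What to change.** Amend section 9.3.3 as follows.

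1. Base the MDMA-attributed change-from-baseline estimates (HR, SBP, DBP and QTcI by time point) on the fasted sessions, noting that readings after 4 hours may follow a meal.
2. Report fed sessions separately, labelled as the combined effect of MDMA and the test meal.
3. Include fed/fasted condition in the concentration-QTc mixed model. Because a constant shift may not suffice, add condition-by-time, either in the main model or as a sensitivity analysis.
4. State that the fed-minus-fasted safety difference is the total effect of dosing with a meal and is not evidence that food changes MDMA's own cardiovascular effect.

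The baseline need not move. A post-meal reading would remove only the part of m already present at that moment. Used as the fed-session baseline, it would also subtract part of the food effect that the study sets out to compare.

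The change is to analysis wording only, with no new measurements. The cost is precision: the main MDMA estimate uses one session per participant, so its standard error may grow by a factor of up to about 1.4, and by less if a participant's two sessions are positively correlated.
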